summarize the transcript in the form of a clinical note. Early implementations of these models show promise in reducing documentation burden, enhancing patient satisfaction, and improving physician engagement (12-17). However, the implementation of ambient AI scribe technologies raises specific challenges, including variability in performance across different clinical environments, potential equity implications for safety net providers who may not be able to afford these technologies, and uncertainty in their cost-effectiveness.(18) In addition, there are concerns about the use of LLMs use in healthcare, including the loss of nuanced clinical reasoning and hallucinations in AI-generated notes, which could inadvertently increase physician documentation time and burnout. These challenges underscore the importance of rigorous empirical evaluations of ambient AI scribes.(19)

To our knowledge, no studies have conducted a randomized controlled trial (RCT) of ambient AI scribe vendors compared with a usual-care control group. Head-to-head comparison of two ambient AI scribe tools adds to the novelty of this trial. In accordance with the Standard Protocol Items: Recommendations for Interventional Trials–Artificial Intelligence (SPIRIT-AI) guidelines, this study aims to evaluate the effect of two separate ambient AI scribes on reducing physician documentation time, mitigating burnout, and enhancing productivity.(20) We hypothesize that each tool will be associated with significant reductions in time-in-note as well as physician burnout rates.

Methods

Study Aims

The primary aim of this study is to evaluate the impact of two ambient AI scribe technologies on physician change from baseline time spent on EHR documentation, comparing each scribe to a control group. Secondary objectives include assessing the ambient AI scribes' impact on physician metrics such as burnout, physician satisfaction, perceived harmful consequences, and productivity. Additionally, the study team intends to perform an economic evaluation analysis of the tools to guide business decision making.

Participants

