Secondary outcomes include burnout scores from the Mini-Z 2.0, provider task load adapted from the NASA Task Load Index, Professional Fulfillment Index scores, and the Net Promoter Index.(21-23) Additional outcomes include self-reported satisfaction with the documentation method, self-reported effects on note accuracy, patient safety, equity, and other potential unintended consequences, such as hallucinations, harmful, or poor-quality transcriptions. The study team is also recording physician-level billing information via RVU and clinic turnover rate to determine changes in productivity. We will examine change in additional Signal metrics including pajama time per scheduled day, time outside scheduled hours per scheduled day, and number of unscheduled days where time is spent in the system.

Data Collection Methods

The study dataset includes both data already collected via a pre-implementation survey and post-interventional data comprised of Epic data and a follow-up survey. The pre-implementation survey, sent to providers in all three arms through Qualtrics one month prior to implementation, confirmed eligibility and opt-in to the trial. Questions included

baseline assessment of the Mini-Z 2.0, provider task load, and Professional Fulfillment index, as well as provider demographic questions. Post-intervention data collected immediately after implementation will include efficiency metrics provisioned by Epic via its Signal platform, follow-up survey responses, provider-level professional billing information, and encounter-level time data. The follow-up survey will also capture physician-reported effects on note accuracy, patient safety, equity, and other unintended consequences, such as hallucinations or errors in transcription. No patient health information is collected in this study. Table 1 outlines each measured outcome, and the corresponding method used for data collection.

Statistical Analysis

This study protocol follows SPIRIT-AI and CONSORT-AI guidelines for development and reporting. Descriptive statistics will be used to characterize the demographics and baseline information of providers in each arm.

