The primary analysis will evaluate the impact of each intervention arm (Vendor A and Vendor B) compared to the control group. Specifically, the two primary comparisons are (1) Vendor A vs. Control and (2) Vendor B vs. Control. The primary outcome, the change in second month's (log-transformed) time in notes per note from the provider's prior six-month baseline, will be analyzed using a linear mixed-effects model. This model will include a study arm effect, a period effect (second vs. first month), and their interaction. Random physician effects will account for multiple timepoints per provider, and linear contrasts will evaluate differences between arms at the second month timepoint. We are

studying the period effect under the assumption that first month represents a learning phase and may not accurately reflect potential efficiency gains, while second month reflects proficiency with the tool. A two-sided 0.025 significance level (2-fold Bonferroni correction) will be used to account for multiple testing in the primary hypothesis tests.

Secondary outcomes will include measures such as burnout scores, task load, and professional fulfillment. These outcomes will be analyzed using similar statistical approaches, including comparisons of Vendor A and Vendor B to the control group, as well as an exploration of the relative impacts of Vendor A and Vendor B.

Our economic evaluations will entail a cost consequence analysis and a budget impact analysis.(24, 25) The cost-consequence analysis will separately present costs and outcomes associated with each intervention arm compared to the control arm. This analysis will show incremental costs as well as incremental benefits of each ambient AI scribe tool compared to the control group. The budget impact analysis will estimate the financial impact, from the perspective of the health system, of varying levels of implementation of each ambient AI scribe tool and project any potential gains in revenues through improvement in physician productivity and documentation efficiency.(24)

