 370 were excluded due to ineligibility, declining participation, incomplete surveys, or decision-
 371 making roles. The remaining 238 participants were randomized into three arms: Vendor A (n
 372 = 80), Vendor B (n = 79), and Control (n = 79). The study spans a two-month intervention
 373 period, with follow-up and analysis monitoring dropout counts due to discontinued
 374 intervention or insufficient data availability

375

Study Period	Enrollment	Allocation	Study Period
Timepoint	-1 month	- month	2 months
	Oct 2024	Nov 4, 2024	Nov 4, 2024 – Jan 3, 2025
Enrollment			
Eligibility Screen	X		
Informed Consent	X		
Randomization		X	
Interventions			
Vendor A or B			X
Control (Arm C)			
Provider-based Assessments^Φ			
Time in Notes per note (primary) [†]		X	X
Pajama time			X
After-hours (7 PM– 7 AM)			X
Mini-Z 2.0 Burnout Score	X		X
Professional Fulfillment Index	X		X
NASA Task Load	X		X
Physician Satisfaction	X		X
Net Promoter Score			X
Appointment Turnover Time			X
Relative-Value Units (RVU) per clinic			X

^Φ Change from baseline

[†] The primary outcome for 'Time in Notes per Note' is the second month (Dec 3, 2024 – Jan 3, 2025), though data from the entire study period are analyzed to evaluate period effects.

Table 1 – SPIRIT-AI Schedule of enrollment, interventions, and assessments outlining key study activities, including eligibility screening, consent, randomization, interventions, and outcome assessments. Primary and secondary measures, such as time in notes per note, burnout scores, task load, and productivity metrics, are collected at specified intervals during the enrollment, allocation, and study periods (October–December 2024)

References

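### Survey secondaries: as documented, an unadjusted change comparison, unbiased but less precise than baseline-adjusted ANCOVA; Net Promoter Score has no baseline from which to compute a change

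*Combined protocol and SAP*

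**What the plan says.** **Survey model.** The Statistical Analysis section introduces these outcomes with "Secondary outcomes will include measures such as burnout scores, task load, and professional fulfillment" and continues "These outcomes will be analyzed using similar statistical approaches, including comparisons of Vendor A and Vendor B to the control group", adding an exploration of Vendor A against Vendor B. It names no model, covariate or significance level for them.

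**The model it points to.** The sentence on the primary analysis model reads: "the change in second month's (log-transformed) time in notes per note from the provider's prior six-month baseline, will be analyzed using a linear mixed-effects model". The terms follow: "This model will include a study arm effect, a period effect (second vs. first month), and their interaction". Then: "Random physician effects will account for multiple timepoints per provider". No baseline value is listed as a covariate. Nor are the three variables used in the covariate-constrained randomization (baseline time in notes, burnout score, clinic days per week; Study Design and Randomization).

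**Scale and timing.** The footnote to the provider-based assessments in Table 1 reads "Change from baseline" and covers the whole block, Net Promoter Score included. Mini-Z, Professional Fulfillment, task load and satisfaction are marked at enrollment and in the study period. Net Promoter Score is marked in the study period only. Data Collection Methods describes the pre-implementation survey as "baseline assessment of the Mini-Z 2.0, provider task load, and Professional Fulfillment index" plus demographics. Intervention and Implementation schedules one post-implementation survey, at the end of the two months.

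**Hypothesis.** The Background expects "significant reductions in time-in-note as well as physician burnout rates". Secondary Outcomes, Statistical Analysis and Table 1 all refer to burnout scores.

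**The concern.** The primary model is built for two post-baseline months per physician. The surveys have one follow-up, so that model cannot be fitted to them as written. What survives is a comparison of mean change between each vendor and control, with nothing adjusted for. Burnout is in the trial's title and its hypothesis, so the precision of this analysis matters. The baseline survey had to be completed before randomization, so the Mini-Z, task load and fulfillment baselines exist for every randomized physician and adjustment needs no new data.

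Net Promoter Score is a listed secondary under a change-from-baseline label but has no scheduled baseline. The control arm has no scribe, and the documents do not say what its physicians would be rating.

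**Working it through.** **1. The plan's own figure.** The only power statement (Sample Size) is for the primary outcome: 79 per condition, 80% power, 0.50 SD, two-sided 0.025, two-sample t-test.

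- Normal approximation: n = 2(2.2414 + 0.8416)² / 0.50² = 76.04, so 77 per arm.
- Noncentral t: 77.3, so 78 per arm.
- At 79 per arm, power is 81.6% (normal) or 80.9% (t), and the detectable effect is 0.495 SD.

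The figure reproduces. Nothing here is an arithmetic error in the plan.

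**2. Which primary terms carry over to a survey score.** One baseline and one follow-up give one change score per physician.

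| Term in the primary model | Survey change score |
|---|---|
| Arm | carries over |
| Period (month 2 vs month 1) | no second period |
| Arm × period | not estimable |
| Random physician effect | not separable from residual error |
| Baseline value, randomization covariates | not listed |

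Only arm remains, which is an unadjusted comparison of mean change.

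**3. Cost in precision.** Let σ² be the variance of the score, equal before and after, and ρ the pre-post correlation.

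- Variance of change: 2(1−ρ)σ²
- Residual variance after ANCOVA: (1−ρ²)σ² = (1−ρ)(1+ρ)σ²
- Ratio, ANCOVA to change: (1+ρ)/2

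The documents give no SD or ρ for any survey score, so a range is shown. Detectable effects are 0.4945 × √variance in raw-score SD, with 79 per arm, complete follow-up and 80% power. The two-sided 0.025 level is borrowed from the primary tests, since none is stated for secondaries.

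| ρ (assumed) | Variance ratio | Reduction | 79 per arm by ANCOVA is worth, analysed as change | Detectable effect, change | Detectable effect, ANCOVA | Power at 0.40 SD, change → ANCOVA |
|---|---|---|---|---|---|---|
| 0.3 | 0.65 | 35% | 79/0.65 = 122 | 0.585 | 0.472 | 45% → 65% |
| 0.5 | 0.75 | 25% | 79/0.75 = 105 | 0.495 | 0.428 | 60% → 74% |
| 0.7 | 0.85 | 15% | 79/0.85 = 93 | 0.383 | 0.353 | 84% → 89% |
| 0.8 | 0.90 | 10% | 79/0.90 = 88 | 0.313 | 0.297 | 96% → 97% |

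Below ρ = 0.5 the variance of change exceeds σ², so change is then less precise than the follow-up score alone (0.585 against 0.495 SD at ρ = 0.3).

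**4. Net Promoter Score.** The places that bear on it, side by side:

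- Secondary Outcomes lists it.
- The Table 1 footnote makes it a change from baseline.
- Table 1 gives it no enrollment mark.
- The described content of the baseline survey does not include it.

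As scheduled, no change can be computed. A follow-up comparison of Vendor A with Vendor B can be.

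**5. Satisfaction.** Table 1 marks it at enrollment, but Data Collection Methods does not name it among the baseline items. Whether a baseline value exists has to be confirmed.

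**The case against.** **The plan never says unadjusted.** True. A reader might infer that the plan deliberately rejects baseline adjustment. The documents do not support that: the reading rests on the listed terms, the Table 1 label and silence about covariates. One could also fit a mixed model to the baseline and follow-up scores and call it similar. But with complete data and unconstrained baseline means, its arm-by-time contrast is the difference in mean change, so the precision is that of the change score. The efficiency point stands.

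**The baseline is not thrown away, and nothing is biased.** Both correct. A change score uses the baseline. Regression to the mean is expected equally in all arms under randomization, so it does not distort the contrast. The burnout score was also balanced by design. For burnout the two point estimates should therefore lie close together, and the power figures above, which take simple randomization, are approximate. An unadjusted analysis would still take its standard error from the larger variance of change. Task load, fulfillment and satisfaction were not themselves balanced. This is a loss of precision, not of validity.

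**The loss may be small.** It may. At ρ = 0.8 it is 10% of variance and hardly moves power.

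**Net Promoter Score can still be analysed.** Correct. A reader might infer that no analysis is possible, but the Statistical Analysis section already foresees comparing the two vendors. That paragraph does not name Net Promoter Score, and the item wording is not given, so control physicians may have rated their usual method. A missing baseline mark alone is not conclusive either: pajama time lacks one too, although EHR data were collected from six months before go-live. A survey item that was not asked cannot be recovered in that way, however, and the described baseline content does not include it.

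**Burnout rates.** A reader might infer a planned, badly underpowered test of proportions. No such test is planned. Outcome definition, analysis section and Table 1 all use scores, so only the hypothesis wording needs alignment.

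**Conclusion.** The point holds as one of efficiency and specification. As documented, the survey secondaries reduce to an unadjusted comparison of change. ANCOVA on a baseline already collected would lower the variance by 10% to 35% for ρ from 0.8 to 0.3, assuming equal pre and post variances. The actual size cannot be fixed from the documents, because they give no ρ. The stronger readings, that the burnout comparison is biased or that the baseline is discarded, do not hold.

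For Net Promoter Score the change-from-baseline label cannot apply as scheduled. A comparison with control is undefined unless control physicians were given something to rate. This should be corrected, but it does not touch the primary analysis.

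**What to change.** - **Survey scores.** State an ANCOVA for each: follow-up score on arm, its own baseline score and the three randomization covariates (baseline time in notes, burnout score, clinic days per week). For burnout, if the score used in the randomization is the Mini-Z score, it enters once.
- **Satisfaction.** Confirm that a baseline item exists. If not, drop the change label and omit the own-baseline term.
- **Net Promoter Score.** Remove it from the change-from-baseline block. State who answered the item and about what. Report it at follow-up only, as Vendor A versus Vendor B, and add control only if control physicians rated their usual documentation method.
- **Hypothesis.** Replace burnout rates by burnout scores.

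The cost is wording in the Statistical Analysis section, Table 1 and the Background, with no new data for Mini-Z, task load or fulfillment. It is not purely editorial, though. The document is dated January 28, 2025 and the trial period ended on January 3, 2025, so the change comes after the intervention period. It should be dated and declared, with a statement of whether survey results by arm had been seen.

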Eligible participants for this study included ambulatory care physicians across multiple specialties within the UCLA Health system who held at least one half-day of clinic per week. Trainee providers (e.g., residents, medical students) and allied healthcare professionals (e.g., RNs, PAs) were excluded, along with attendings who work exclusively with trainees and provide no direct patient care. Only English-language encounters are included due to a lack of internal validation for translation capabilities in the vendor technologies. Physicians who typically use a human scribe agreed to forego this assistance while assigned to an intervention or control group. Due to the technical requirements of one vendor, all providers are required to use an iOS portable device.

Participants were recruited based on specific department leadership suggestions and non-specific department-wide emails, resulting in 331 provider invitations. Of these, only 238 met the study criteria. Reasons for exclusion included ineligibility (e.g., did not meet inclusion criteria; $n = 7$), refusal to participate ($n = 21$), status as a key decision-maker (to prevent potential conflicts of interest in outcome assessment; $n = 20$), or failure to

complete the baseline survey (n = 43). Participants who met eligibility requirements and agreed to participate were required to complete a pre-implementation survey prior to randomization.

Study Design and Randomization

Eligible physicians (n = 238) were randomized into one of three groups: either of the two ambient AI scribe technologies (Vendor A or Vendor B) or a control group with no scribe (Figure 1). Randomization followed a 1:1:1 allocation over a two-month period and analysis will follow an intention-to-treat approach. Since both vendor tools are being rolled out from November 4, 2024 to January 3, 2025, secular trends, seasonal variations, and clinic holiday closures are accounted for by comparing effects of Vendor A and Vendor B with results from a contemporaneous control group.

Covariate-constrained randomization was conducted by the trial statistician to balance participants' baseline geometric mean time in notes per note collected over the prior year, as well as burnout scores and clinic days per week obtained from survey data.

Intervention and Implementation

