We will perform pre-specified secondary subgroup analyses to investigate heterogeneous treatment effects by introducing interactions between primary model terms and potential effect modifiers. Specifically, these analyses will evaluate whether weekly clinic days, provider sex, and the proportion of visits from new vs. established patients moderate the intervention effects. These analyses will be conducted to meet out hypothesized differences in effects due to higher baseline burnout rates in women, an

246 anticipated bigger dose response in physicians with more visits per week, and higher
247 utilization for new patients where previous note text cannot be copied forward.

249 *Sample Size*

250 The sample size for this study is constrained by exclusion criteria and a contractual
251 limitation allowing at most 100 concurrent users of any given tool. A sample size of at least
252 79 providers per condition will provide 80% power to detect effect sizes as small as 0.50
253 standard deviations, assuming a two-sample t-test and a two-sided 0.025 significance
254 level. This is a conservative simplification of the planned linear mixed-effects regression
255 analysis.

256 Using pre-study data from a comparable timeframe, the estimated log-scale
257 standard deviation of change for the time in notes per note metric is approximately 0.31.
258 This design will be powered to detect a 15.5% relative improvement in the primary
259 outcome. Given a baseline-year geometric mean time in notes per note of approximately
260 4m 43s, this corresponds to an absolute difference of roughly 44 seconds. This effect size
261 falls within the range of those seen in the literature(17).

263 **Discussion**

264 Our study aims to evaluate the impact of ambient AI scribes on EHR utilization,
265 physician burnout, and billing capture in the ambulatory setting through a three-arm RCT
266 over a 2-month period. The study is the largest RCT of ambient AI scribes to date and first to

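### The dose-response subgroup hypothesis concerns visits per week, but the modifier named to test it is weekly clinic days

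*Combined protocol and SAP*

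**What the plan says.** The subgroup paragraph of Statistical Analysis proposes to study effect modification by "introducing interactions between primary model terms and potential effect modifiers". The analyses will "evaluate whether weekly clinic days, provider sex, and the proportion of visits from new vs. established patients moderate" the intervention effects. The next sentence gives one reason per modifier:

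- **Sex:** "hypothesized differences in effects due to higher baseline burnout rates in women".
- **Volume:** an "anticipated bigger dose response in physicians with more visits per week".
- **New-visit share:** greater use of the tool for new patients, whose notes have no earlier text to carry forward.

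The primary model, defined earlier in the same section, has as its outcome "the change in second month's (log-transformed) time in notes per note from the provider's prior six-month baseline". Its terms are arm, period and their interaction. For the secondary outcomes, burnout among them, the section says: "These outcomes will be analyzed using similar statistical approaches".

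Study Design and Randomization gives the source of the clinic-days variable. Allocation balanced baseline time in notes "as well as burnout scores and clinic days per week obtained from survey data". Visits per week appears in the abstract as a productivity outcome. It is not among the modifiers, and neither the Secondary Outcomes section nor Table 1 lists it.

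**The concern.** A subgroup analysis is informative when the modifier measures the thing the hypothesis is about. Here the hypothesis is that physicians with more encounters gain more, and the modifier counts days.

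The two can part company in this sample. Participants come from multiple specialties, eligibility starts at one half-day of clinic per week, and the Discussion notes that sessions run from half to full days. Two physicians with the same number of clinic days may see quite different numbers of patients.

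A null clinic-days interaction could then mean either no dose response or a proxy too coarse to show one. A positive interaction is not clean either, because the Discussion links clinic schedule to the time needed to integrate the tool. That is a different route from encounter volume.

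The sex modifier raises a smaller question of scope. Its rationale is about burnout, but the interactions are described as additions to the primary model, whose outcome is documentation time.

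**Working it through.** **The plan's own figure.** The only power statement is for the main comparisons: 79 per arm, 0.50 SD, two-sided 0.025, 80% power. It reproduces. The normal approximation gives 77 per arm and power 0.816 at 79. The exact two-sample t-test gives 78 per arm (77.3 before rounding) and power 0.809 at 79. No power or significance level is stated for the subgroup analyses.

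**Matching each modifier to its hypothesis.**

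| Modifier named | Hypothesis given | Match |
|---|---|---|
| Weekly clinic days | Larger effect with more visits per week | Indirect: days stand in for visits |
| Provider sex | Effects differ by sex because of women's higher baseline burnout | Direct for sex on time in notes; burnout outcome not mentioned; baseline burnout not a modifier |
| Share of new vs. established visits | More use for new patients | Direct; measurement window not stated |

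**Illustration 1: cost of the proxy.** Suppose all modification runs linearly through visits per week, clinic days correlate r with visits, and the residual SD is unchanged. The slope difference per SD of clinic days is then r times that per SD of visits, so the proxy retains r² of the information. Start from a hypothetical 80% power at two-sided 0.05 (both assumed):

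power = 1 − Φ(1.96 − r × (1.96 + 0.8416))

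- r = 0.9: information 0.81, power 0.71
- r = 0.8: information 0.64, power 0.61
- r = 0.7: information 0.49, power 0.50

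**Illustration 2: anchored to the arm size.** Take 79 per arm, one vendor against control, and an assumed slope difference of 0.50 SD of outcome per SD of visits. Power is Φ(0.50 × r / √(2/79) − 1.96):

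- r = 1: 0.881
- r = 0.9: 0.807
- r = 0.7: 0.595
- r = 0.5: 0.349

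The direction is the same, but the level differs because the assumed slope differs. With a slope difference of 0.25 SD, power is only 0.349 even at r = 1.

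**Sex interaction, for context.** With a share w of women, SE = √(2/(79w) + 2/(79(1 − w))) in SD units. For w = 0.5 this is 0.318, and for w = 0.3 it is 0.347 (shares assumed). Power for a 0.50 SD difference in effect at two-sided 0.05 is 0.349 and 0.302. The difference detectable with 80% power is 2.80 × SE, or 0.89 and 0.97 SD. These analyses have limited power in any case, which makes a null result through a proxy harder to read.

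**The case against.** The best defence of clinic days is practical. It is measured before randomization, it was balanced by the constrained allocation, and it is a direct component of weekly volume. The Discussion also gives clinic schedule a relevance of its own through adaptation time. Visits per week, by contrast, appears only in the abstract, as an outcome, and no baseline collection of it is described. Counted after randomization, it could itself be changed by the tools. All of this stands. It is why the replacement must be a pre-go-live count and why clinic days should be kept. It does not make days the quantity named in the hypothesis.

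On sex, a reader might infer that the hypothesis is never tested, and so that two of the three subgroup analyses miss their target. The documents do not support this. The text hypothesizes that effects differ and gives women's higher baseline burnout as the reason; it does not say that burnout scores will improve more in women. A sex interaction on time in notes does test whether that effect differs by sex. Nor is a sex-by-arm analysis of burnout excluded, since secondary outcomes are to be handled by similar methods. What remains is that the plan does not say which outcomes the interaction covers.

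It can also be said that the power figures are built on assumptions throughout. That is right.

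**Conclusion.** The point holds for one of the three modifiers. Clinic days is an indirect and unjustified stand-in for the visits per week named in the dose-response hypothesis. For sex, the analysis does test a difference in effect on time in notes; the gap is one of scope, because coverage of Mini-Z burnout is unstated and baseline burnout, though measured, is not listed as a modifier.

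The size of the loss is unknown. The fall from 80% to about 50% to 71% rests on an assumed correlation of 0.7 to 0.9, an assumed two-sided 0.05, a hypothetical starting power, and modification acting linearly through visits alone. It should not be cited as the trial's actual loss of power. The matter is minor: it concerns how secondary subgroup results can be read, and the two primary vendor-versus-control comparisons are untouched.

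**What to change.** 1. Name continuous visits per week, from the six months before go-live, as the dose modifier. Do not use the count during the trial. Keep weekly clinic days as a supportive modifier.
2. Take the new-visit proportion from the same pre-go-live window and say so.
3. State which outcomes the sex interaction covers. As an exploratory addition, fit the sex-by-arm term for Mini-Z burnout and, if baseline burnout is the supposed mechanism, a baseline-burnout-by-arm term.

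The cost is a few lines of SAP text, extraction of baseline visit counts, and one more exploratory model for the dose question. The new-visit proportion already needs visit counts, so the added extraction should be small. The burnout models in item 3 use data already collected. Trial Status records that the intervention period ended on January 3, 2025, so any change made after outcomes have been seen by arm should be labelled as a later addition.
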